6.6.4.2. ELISpot response

These analyses will be presented using the Immunogenicity analysis set both overall and separately by whether participants had or did not have an observed PSA response.

Average background-subtracted antigen-specific IFNg ELISpot response (SFU/10⁶ PBMC) will be presented for each stimulation antigen (PSA, PAP, 5T4, STEAP1). Descriptive statistics including n, mean, standard deviation, median, minimum, maximum, and 95% CI for the median based on order statistics will be presented for absolute values, change from baseline, and fold change from baseline at all planned time points (Days 1, 29, 36, 57, 64, 91 and Months 8 and 12). Fold change for values i and j is defined as:

$$(\text{Value j}/\text{Value i})-1.$$

Where value j is the IFNg ELISpot response value at a non-baseline timepoint and value i is the cytokine expression value at day 1. When value i is 0 a small constant, λ , will be added to the calculation. $\lambda=0.5\times\min(\text{non-zero value for all participants at all time points})$. In this case fold change will be calculated as:

$$((\text{Value j} + \lambda)/(\text{Value i} + \lambda))-1.$$

To identify statistically significant differences between baseline and Days 35 and 64, a Wilcoxon signed-rank test using change from baseline will be performed for PSA responders and for non-responders for each stimulation antigen.

Like the graphical summaries described for the ICS analysis, for average background-subtracted antigen specific IFNg ELISpot response (SFU/10⁶ PBMC) a dot plot will be presented by planned time point separately for each stimulation antigen (PSA, PAP, 5T4, STEAP1).

A stacked bar chart will also be displayed for the median total (pooled over antigens) response (SFU/10⁶ PBMC) by planned time point for PSA responders and non-responders.

In addition, a line plot of mean \pm SD of the total (pooled over antigens) response (SFU/10⁶ PBMC) for each treatment will be displayed by planned time point.

A summary of the number and percentage of participants who meet the responder criteria (i.e., those with a background-subtracted average result greater than the positivity threshold) will be presented at all planned time points.

The average background-subtracted antigen-specific IFNg ELISpot responses (SFU/10⁶ PBMC) will be listed by stimulation antigen for each participant at each time point.

6.7. Safety

All participants are to remain on study through month 6 or the start of new therapy, such as ADT, or until development of unequivocal metastatic prostate cancer. Consequently,

adverse event collection will be discontinued for participants who discontinue from follow-up after the start of new therapy.

6.7.1. Extent of Exposure

Duration of exposure will be defined in days as:

$$\text{Exposure (days)} = [\text{date of last dose} - \text{date of first dose}] + 1$$

Number and percentage of participant with the following treatment exposure will be calculated:

- 1 ChAdOx1-PCAQ dose only
- 1 ChAdOx1-PCAQ dose + 1 MVA-PCAQ dose
- 1 ChAdOx1-PCAQ dose + 2 MVA-PCAQ doses
- 1 ChAdOx1-PCAQ dose + 3 MVA-PCAQ doses

The number and percentage of participants where the 1st MVA dose was and was not received within the protocol-defined window (Days 27 to 31 from first dose), the 2nd MVA dose was and was not received within the protocol-defined window (Days 55 to 59) and where all planned MVA doses were received within the protocol-defined windows will be presented. Because the timing of the optional third MVA dose is variable depending on when PSA progression occurs, it will not be considered when summarizing timing of the dose relative to protocol windows. Participants whose 2nd dose of MVA was delayed due to study pause will be included in the denominator for 2nd MVA dose (but will be excluded from numerator as dose was received outside protocol-defined window).

Study treatment administration data will be listed for the Safety Analysis Set. The listing will include date/time of administration, the number of days since the previous study dose, the IMP type (ChAdOx1 vs MVA), the route of administration, the planned and total dose and whether the drug was given as per protocol and details if it was not including other specified information.

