1.3 Schedule of Assessments

Table 1 Schedule of Assessments during the Screening and Intervention Periods

| Visit/Call | Screening Period (42 d) ^a | Intervention Period (Days) | | | | | | | | | | | | |
|---|--------------------------------------|----------------------------|----------------------|----------------------|---------------------|---------------------|-----------------------|---------------------|---------------------|----------------------------------|------------------------------------|----------------------------------|----------------------------------|---------------------|
| | | Day 1 Dosing Visit | Day 2 Telephone Call | Day 8 Telephone Call | Day 15 Clinic Visit | Day 29 Dosing Visit | Day 30 Telephone Call | Day 36 Clinic Visit | Day 43 Clinic Visit | Day 57 Dosing Visit ^k | Day 58 Telephone Call ^k | Day 64 Clinic Visit ^k | Day 71 Clinic Visit ^k | Day 91 Clinic Visit |
| Window ^b | | | 1-2d post-dose | ±1d | ±2d | ±2d | Up to 2d post-dose | ±2d | ±2d | ±2d | Up to 2 d post-dose | ±2d | ±2d | ±2d |
| Informed consent | X | | | | | | | | | | | | | |
| Baseline/eligibility variables | | | | | | | | | | | | | | |
| Demographics | X | | | | | | | | | | | | | |
| Inclusion and exclusion criteria | X | | | | | | | | | | | | | |
| Full physical examination including height and weight | X | | | | | | | | | | | | | |
| Medical and disease history | X | | | | | | | | | | | | | |
| ECOG performance status | X | | | | | | | | | | | | | |
| Historic tumour sample collection ^e | | X | | | | | | | | | | | | |
| Laboratory eligibility and safety tests and investigations | | | | | | | | | | | | | | |
| 12-lead ECG ^c | X | X (pre-dose) | | | X | X (pre-dose) | | | X | X (pre-dose) | | | X | X |
| Echocardiogram ^d | X | | | | | | | | | | | | | |

Optional schedule to be repeated for participants receiving a third dose of MVA-PCAQ after initial PSA response followed by progression. Schedule to be repeated for participants whose 2nd dose of MVA was delayed.¶

Optional schedule to be repeated for participants receiving a third dose of MVA-PCAQ after initial PSA response followed by progression. Schedule to be repeated for participants whose 2nd dose of MVA was delayed.¶

| Visit/Call | Screening Period (42 d) ^a | Intervention Period (Days) | | | | | | | | | | | | |

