|--|--------------------------------------|----------------------------|----------------------|----------------------|---------------------|---------------------|-----------------------|---------------------|---------------------|----------------------------------|------------------------------------|----------------------------------|----------------------------------|---------------------|
| | | Day 1 Dosing Visit | Day 2 Telephone Call | Day 8 Telephone Call | Day 15 Clinic Visit | Day 29 Dosing Visit | Day 30 Telephone Call | Day 36 Clinic Visit | Day 43 Clinic Visit | Day 57 Dosing Visit ^b | Day 58 Telephone Call ^b | Day 64 Clinic Visit ^b | Day 71 Clinic Visit ^b | Day 91 Clinic Visit |
| Prior and concomitant medications | | <=====→ | | | | | | | | | | | | |
| Efficacy assessments | | | | | | | | | | | | | | |
| Serum PSA | X | X | | | | X | | | | X | | X | | X |
| Radiological assessment | X ⁱ | | | | | | | | | | | | | |
| Immunogenicity assessments | | | | | | | | | | | | | | |
| Blood for PBMC assessment ^j | | X | | | | X | | X | | X | | X | | X |
| Blood for ctDNA assessment | | X | | | | | | | | | | | | X |
| Blood for PSA-binding antibody/anti-vector antibody/anti-antigen antibody assessment | | X | | | X | X | | | X | X | | | X | X |

Abbreviations: AESI – Adverse Event of Special Interest, C3=Cohort 3, ChAd=ChAdOx1-PCAQ, CRP=C-reactive protein, CT=computed tomography, ctDNA=circulating tumour DNA, d=day(s), ECG=electrocardiogram, ECOG=Eastern Cooperative Oncology Group, MVA=MVA-PCAQ, MRI=magnetic resonance imaging, PBMC=peripheral blood mononuclear cells, PET=positron emission tomography, PSA=prostate-specific antigen, SAE=serious adverse event

^a If the screening period is longer than 42 days, the participant must be reconsented. Consult with the Medical Monitor for which assessments should be repeated.

^b Windows during the intervention period are calculated from the date of the previous VTP-850 dose.

^c If a cardiac event is reported, blood should be taken for an additional assessment of troponin T and the participant should undergo an additional ECG and echocardiogram at the earliest opportunity.

^d Historic echocardiogram may be used if performed within 3 months of Day 1.

^e May be retrieved at any time during the intervention period.

^f If troponin T test result is abnormal, a re-test on the following day is required.

^g Pre-dose and approximately 30 min post-dose.

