4 TRIAL DESIGN

4.1 Overall Trial Design

This is a multicentre, Phase 1/2, open-label clinical trial of the VTP-850 prime-boost immunotherapeutic in men with biochemical recurrence after definitive local therapy for prostate cancer. The trial will be conducted in up to 30 centres worldwide.

Participants in all cohorts will receive the ChAdOx1-PCAQ component on Day 1 (prime) and the MVA-PCAQ component on Days 29 and 57 (boosts). Participants will be followed until the Month 6 Visit or start of new therapy such as ADT or until development of unequivocal metastatic prostate cancer. Participants who have a PSA response will be followed for an additional 18 months, up to 24 months from first dose, or until start of new therapy such as ADT or development of unequivocal metastatic prostate cancer. In the event that a participant experiences a confirmed PSA response but subsequently experiences PSA progression more than 2 months after their final dose of VTP-850, an additional dose of MVA-PCAQ may be offered to the participant.

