6.11 Contraindications/Delay to Dosing

If the participant has an acute illness (moderate or severe illness with or without fever) or a fever (temperature $\geq 38.0^{\circ}\text{C}$) at the scheduled time or within 48 h before VTP-850 is to be administered, administration of the relevant component should be temporarily delayed. Trial intervention may be administered to that participant once the condition(s) has/have resolved, even if subsequent administration of components of VTP-850 will fall outside of the visit windows specified in the relevant SoA (Table 1). Delays in VTP-850 administration should be discussed with the Medical Monitor so that the optimal timing of administration and subsequent assessments can be agreed upon. See [Section 7.1](#) for permanent discontinuation of trial intervention.

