5.1. Time Points and Visit Windows

5.1.1. General Definitions

During the intervention period, assessment days are calculated relative to the date of the previous VTP-850 dose. During the screening, short-term and long-term follow-up periods, all assessment days will be relative to the first dose of treatment including assessments prior to the first dose of treatment.

During the screening, intervention, short-term and long-term follow-up periods, Day 1 is defined as the first dose of treatment except for the calculation of study windows described in Section 5.1.4 where, during the intervention period, day 1 will be defined relative to the first, second, third and optional fourth dose of VTP-850. Relative days after Day 1 are calculated as (assessment date – Day 1 date) + 1. Relative days prior to Day 1 are calculated as (assessment date – Day 1 date). The day prior to Day 1 is Day -1. There is no Day 0.

The date of the first dose of treatment for each participant will be taken from the ChAdOx1-PCAQ Administration eCRF page. The date of the last dose of treatment for each participant will be the latest date from the ChAdOx1-PCAQ administration or MVA-PCAQ administration eCRF pages.

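### SAP 6.7.1 tests the second MVA dose against fixed Days 55 to 59, but the protocol counts that window from the previous dose

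*SAP*

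**What the plan says.** **SAP 6.7.1 (Extent of Exposure)** plans a table of dose timing. For the first booster it counts participants where "the 1st MVA dose was and was not received within the protocol-defined window (Days 27 to 31 from first dose"). For the second booster it counts participants where "the 2nd MVA dose was and was not received within the protocol-defined window (Days 55 to 59"), with no anchor printed beside the range. A third count covers participants with every planned MVA dose in window. Men whose second MVA dose slipped because of the study pause stay in the denominator but cannot enter the numerator.

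**Protocol Table 1 (section 1.3)** gives the tolerances. The Window row, from the Day 15 to the Day 58 column, reads "2d | ±2d | Up to 2d post-dose | ±2d | ±2d | ±2d | Up to 2 d post-dose", so the Day 29 and Day 57 dosing visits each have ±2 days. That row carries footnote b: "Windows during the intervention period are calculated from the date of the previous VTP-850 dose".

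**SAP 5.1.1** opens with the same principle: "During the intervention period, assessment days are calculated relative to the date of the previous VTP-850 dose". Its next paragraph takes Day 1 as the first dose, except when deriving the study windows of SAP 5.1.4.

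**SAP 4.5** requires in-window dosing for the Per Protocol Set. It prints no day range, and it treats doses delayed by the study pause as in window.

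**The concern.** The SAP attributes its range to the protocol, but the protocol's stated rule gives a different range whenever the first MVA dose is not exactly on Day 29. A dose correctly spaced from its predecessor can be tabulated as out of window, early or late. A dose spaced too closely or too widely can be tabulated as in.

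What is at stake is the accuracy of two planned counts: second MVA dose in window, and all planned MVA doses in window. There is also a risk of inconsistency. Protocol 11.2.5.2 lists visits outside the protocol window as deviations. If these are judged under footnote b, the deviation listing and the exposure table could disagree about the same man. SAP 6.7.1 is the only place in the SAP that puts numbers on the dosing windows, because the tables in SAP 5.1.4 set the Day 29 and Day 57 visits at the dose itself. A programmer could therefore reuse Days 55 to 59 when building the Per Protocol Set.

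**Working it through.** **Inputs**
- Nominal schedule: "the MVA-PCAQ component on Days 29 and 57 (boosts"), Protocol 4.1. The nominal gap between MVA doses is 57 − 29 = 28 days.
- Tolerance: ±2 days at each dosing visit, from the column order of the Window row in Protocol Table 1.
- Anchor: the previous dose, Protocol Table 1 footnote b.
- Day numbering: "Relative days after Day 1 are calculated as (assessment date – Day 1 date) + 1", SAP 5.1.1, so the first dose is Day 1.

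**Step 1: reproduce the SAP's figures.** From the first dose, 29 ± 2 = Days 27 to 31 and 57 ± 2 = Days 55 to 59. Both match SAP 6.7.1. Re-anchored to the previous dose, the second range would read Days 27 to 31 again, so Days 55 to 59 can only be a first-dose window. The first MVA dose raises no conflict, because its previous dose is the first dose.

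**Step 2: apply the protocol rule.** If the first MVA dose is on study day d, the window for the second is (d + 28) ± 2, that is, 26 to 30 days after the first MVA dose.

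**Step 3: compare the two rules for every in-window first MVA day.**

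| First MVA day | Protocol window, second MVA | In by protocol, out by SAP | In by SAP, out by protocol (gap in days) |
|---|---|---|---|
| 27 | 53–57 | 53, 54 | 58 (31), 59 (32) |
| 28 | 54–58 | 54 | 59 (31) |
| 29 | 55–59 | none | none |
| 30 | 56–60 | 60 | 55 (25) |
| 31 | 57–61 | 60, 61 | 55 (24), 56 (25) |

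Each rule accepts 5 × 5 = 25 day pairs.
- Protocol-compliant pairs counted out by the SAP: 2 + 1 + 0 + 1 + 2 = 6 of 25. Three are early (27/53, 27/54, 28/54) and three are late (30/60, 31/60, 31/61).
- SAP-accepted pairs outside the protocol window: 2 + 1 + 0 + 1 + 2 = 6 of 25. Three gaps are too long (31, 32 and 31 days) and three too short (25, 24 and 25 days).
- Gaps accepted by the SAP run from 55 − 31 = 24 to 59 − 27 = 32 days, against 26 to 30 under the protocol rule.

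**Step 4: a delayed first MVA dose.** Protocol 6.11 lets a dose postponed for illness be given later, "even if subsequent administration of components of VTP-850 will fall outside of the visit windows specified in the relevant SoA". If the first MVA dose is on Day 34 or later, the protocol window for the second opens at 34 + 26 = Day 60 or later. It then no longer overlaps Days 55 to 59, so every second dose spaced by footnote b is tabulated as out of window.

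**Step 5: weight of one man.** Cohorts 2 and 3 are planned at 6 participants each (SAP Table 2). One misclassified man moves a cohort percentage by 1/6 = 16.7, about 17 points.

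**The case against.** The SAP's numbering can be defended. SAP 5.1.1 takes Day 1 as the first dose and exempts only the windows in SAP 5.1.4. Section 6.7.1 lies outside that exemption, so counting Days 55 to 59 from the first dose is consistent with the SAP's general convention. This stands, and it makes SAP 5.1.1 mixed support. It explains where the numbers come from, but it does not make them the protocol's window, which is how the SAP labels them. The firm conflict is with Protocol Table 1 and footnote b.

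The table is also descriptive, and SAP 6.7.1 provides a per-participant listing that includes the days since the previous dose. In a Phase 1 of about 25 men a reader can recover the true interval. That stands too and keeps the point small, but the listing does not correct the printed counts.

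A reader might go further and infer that the mismatch decides which Phase 1 men are replaced or who joins the 25 assessed at Stage 1, or that it alters efficacy results through the Per Protocol Set. The documents do not support this. Replacement is a conduct rule in the protocol (4.1.1 and 6.12). Entry to the 25 is a Phase 2 matter (Protocol 4.1.2), and the SAP says it covers Phase 1 only. SAP 4.5 does not print Days 55 to 59. No endpoint analysis is assigned to the Per Protocol Set: PSA response uses the Efficacy Evaluable Set, safety the Safety Analysis Set, immunogenicity its own set, and other efficacy the Full Analysis Set.

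**Conclusion.** The point holds as a minor inconsistency in how dose timing is classified. SAP 6.7.1 labels as protocol-defined a window that equals the protocol's only when the first MVA dose is on Day 29. Followed as written, it can misclassify doses in both directions, so the two counts that include the second MVA dose may be wrong.

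The result rests on reading ±2 days from the extracted Table 1 row and on taking the first dose as the unstated anchor for Days 55 to 59, the only reading that fits the numbers. It would be tempting to turn 6 of 25 into an expected 24% of participants. That would need dosing days spread evenly and independently over their windows, and the documents give no distribution of dosing days. If most first MVA doses fall on Day 29, few or no men are affected.

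No safety, PSA or immunogenicity analysis is shown to change. Per Protocol Set membership is affected only if the fixed range is reused for SAP 4.5.

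**What to change.** Reconcile SAP 6.7.1 with Protocol Table 1 and footnote b, and state the anchor next to the range.

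If the table is to report the protocol-defined window, replace the fixed Days 55 to 59 with in/out status derived from the days since the previous dose, using footnote b's rule. Apply the same anchor wherever SAP 4.5 refers to in-window dosing, and keep its exception for doses delayed by the study pause. SAP 6.7.1's separate treatment of those doses can stay as it is.

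This corrects an analysis classification; it does not propose a dosing schedule. The cost is about one line of SAP text in 6.7.1 and a matching clarification in 4.5. The interval is already planned for the listing, so no new data are needed.

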6.7.2. Adverse Events

All AEs recorded on the eCRF will be coded using the MedDRA dictionary [version 25.1 or later]:

- Treatment-emergent AEs (TEAEs) are events with start date on or after the first dose of VTP-850 and reported as not starting before first treatment.
- Treatment-Emergent Serious AEs (TESAEs) will be defined as TEAEs regarded by the investigator as Serious = “Yes”.
- The relationship between a TEAE and VTP-850 is assessed as related or not related. A treatment-related TEAE will be defined as a TEAE considered by the investigator related to treatment.

- Assessment of AE severity / intensity will be based on the National Cancer Institute-Common Terminology Criteria for AEs (NCI-CTCAE⁴, version 5.0). Severe TEAEs are defined as TEAEs assessed as being “Grade 3 / Grade 4 / Grade 5” in intensity.
- TEAEs leading to discontinuation of treatment are defined as TEAEs where “Action Taken With Study Treatment” is indicated as “Drug Withdrawn”.

Adverse events will be summarized for the Safety Analysis Set by treatment group and overall as follows:

- An overview of TEAEs including the number and percentage of participants with at least one of each mentioned TEAE type:
 - Any TEAE
 - Leading to discontinuation of study treatment
 - Leading to death
 - Grade 1 severity (mild)
 - Grade 2 severity (moderate)
 - Grade 3 severity (severe)
 - Grade 4 severity (life-threatening or disabling)
 - Grade 5 severity (death related to TEAE)
 - Any study treatment-related TEAE
 - Leading to discontinuation of study treatment
 - Leading to death
 - Any serious TEAE
 - Leading to death
 - Any serious study treatment-related TEAE
 - Leading to death
- The number and percentage of participants reporting each TEAE and the count of number of events will be summarized by SOC and PT for the following types of TEAEs:
 - TEAEs
 - TEAEs Leading to Discontinuation of Study Treatment
 - TEAEs Leading to Death
 - TEAEs by Maximum Severity
 - Treatment-related TEAEs
 - Treatment-related TEAEs by Maximum Severity
 - Treatment-related TEAEs Leading to Discontinuation of Study Treatment
 - Treatment-related TEAEs Leading to Death
 - Serious TEAEs
 - Serious TEAEs Leading to Discontinuation of Study Treatment
 - Serious TEAEs Leading to Death
 - Study Treatment Related Serious TEAEs
 - Study Treatment Related Serious TEAEs Leading to Death

- Study Treatment Related Serious TEAEs Leading to Discontinuation of Study Treatment
-
- The number and percentage of participants who died will be summarized by the primary reason of death.

In the above summaries, participants with more than one TEAE within a particular SOC are counted only once for that SOC. Similarly, participants with more than one TEAE within a particular PT are counted only once for that PT, respectively. Overall summaries of “Any TEAE” and “Any study treatment-related TEAE” will only include participants at the maximum severity.

For summaries by maximum severity, participants with multiple TEAEs within a particular SOC or PT will be counted under the category of their most severe TEAE within that SOC or PT. TEAEs with missing severity will be included in the counts of the ‘Number of Participants with at least one TEAE’, ‘System Organ Class’ and ‘Preferred Term’ rows of the summary but they will not be included in the counts by severity.

The following tables will also be presented by administration (i.e. ChAdOx1-PCAQ dose, 1st MVA-PCAQ dose, 2nd MVA-PCAQ dose, 3rd MVA-PCAQ dose), for TEAEs that start within 28 days of each administration (e.g. summarizing TEAEs which occurred from ChAdOx1-PCAQ dose up to the earliest of 1st MVA-PCAQ dose or 28 days following the first dose). The denominator will be the number of participants who have received that dose:

- TEAEs
- TEAEs by Maximum Severity
- Treatment-related TEAEs
- Treatment-related TEAEs by Maximum Severity
- Serious TEAEs
- Study Treatment Related Serious TEAEs

Summaries by SOCs and PTs will be sorted by SOCs alphabetically (MedDRA) and PTs within SOC by descending order of total incidence. Where preferred terms tie, PTs will be sorted alphabetically.

No statistical comparisons of AEs between treatment groups will be performed.

All AE data will be listed using the Safety Analysis Set. Treatment-emergence status will be flagged in the listing. The listing will present the relative start and stop day of the AE calculated relative to the first dose of treatment. If the AE is “Ongoing” it will be indicated as such in the listing and the relative stop day will not be calculated.

In addition, the following listings will be presented:

- Listing of Deaths
- Listing of Serious TEAEs
- Listing of AEs Leading to Discontinuation of Study Treatment

